One fatal case of SJS in a clinical trial and one fatal case of TEN in the post-marketing setting have been reported in patients treated with Pembrolizumab. In total 8 cases of SJS and 2 cases of TEN all of which were serious. The risk of SJS and TEN is reported at approximately 0.4 – 7 cases per million patient years in the general adult population. Independent risk factors include certain medications such as anticolvulsants, sulfonamides, aminopenicillins, allopurinol and NSAIDs. Non-medication triggers include infection, contrast media, and vaccinations. Malignancy is associated with an increased mortality rate in patients with SJS and TEN.

Monitor patients for signs and symptoms of SJS and/or TEN, withhold Pembrolizumab and refer patient for specialized care and treatment. Administer corticosteroids for SJS grade 3 or 4 or TEN grade 4 (initial dose of 1-2 mg/kg/day prednisone or equivalent followed by a taper). Permanently discontinue Pembrolizumab for any grade of SJS or TEN.

Immune-Mediated Myocarditis

A total of 6 cases of myocarditis have been reported in patients treated with Pembrolizumab in clinical trials or in expanded access program. One fatal case was reported from a clinical trial. Immune-mediated myocarditis should be suspected if other causes of myocarditis, such as infection or prior radiation therapy, have been excluded. Risk factors include certain medications and treatment modalities such as radiation, anthracycline, alkylating agents and most recently checkpoint inhibitors.

Monitor patients for signs and symptoms of Immune-Mediated Myocarditis and ensure adequate evaluation to exclude the other etiologies. Administer corticosteroids for grade 2 immune-mediated myocarditis (initial dose of 1-2 mg/kg/day prednisone or equivalent followed by a taper). Permanently discontinue Pembrolizumab for grade 3-4 myocarditis or if toxicity does not resolve within 12 weeks of start of grade 2 toxicity or inability to reduce corticosteroid to 10 mg or less of prednisone or equivalent per day within 12 weeks.

Immune-Mediated Pneumonitis

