Other clinically important immune-mediated adverse reactions can occur. The following clinically significant, immune-mediated adverse reactions occurred in less than 1% of patients treated with KEYTRUDA in Trial 1: exfoliative dermatitis, uveitis, arthritis, myositis, pancreatitis, hemolytic anemia, partial seizures arising in a patient with inflammatory foci in brain parenchyma, Guillain-Barré syndrome, vitiligo, encephalitis, and adrenal insufficiency. Across clinical studies with KEYTRUDA in approximately 2000 patients, the following additional clinically significant, immune-mediated adverse reactions were reported in less than 1% of patients: myasthenic syndrome, optic neuritis, rhabdomyolysis and sarcoidosis in parts of the lymph nodes, skin, or lungs.

For suspected immune-mediated adverse reactions, ensure adequate evaluation to confirm etiology or exclude other causes. Based on the severity of the adverse reaction, withhold KEYTRUDA and administer corticosteroids. Upon improvement to Grade 1 or less, initiate corticosteroid taper and continue to taper over at least 1 month. Based on limited data from clinical studies in subjects whose immune-related adverse reactions could not be controlled with corticosteroid use, administration of other systemic immunosuppressants can be considered. Restart KEYTRUDA if the adverse reaction remains at Grade 1 or less. Permanently

discontinue KEYTRUDA for any severe or Grade 3 immune-mediated adverse reaction that recurs and for any life-threatening immune-mediated adverse reaction.

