Hypophysitis	Grade 2	Withhold	Administer corticosteroids and initiate hormonal replacements as clinically indicated.	Monitor for signs and symptoms of hypophysitis (including hypopituitarism and adrenal insufficiency)
	Grade 3 or 4	Withhold or permanently discontinue ¹		

Hyperthyroidism	Grade 2	Continue	Treat with non-selective beta-blockers (eg, propranolol) or thionamides as appropriate	Monitor for signs and symptoms of thyroid disorders.
	Grade 3 or 4	Withhold or permanently discontinue ¹		
Hypothyroidism	Grade 2-4	Continue	Initiate thyroid replacement hormones (eg, levothyroxine or liothyronine) per standard of care	Monitor for signs and symptoms of thyroid disorders.
Nephritis and Renal dysfunction	Grade 2	Withhold	Administer corticosteroids (prednisone 1-2 mg/kg or equivalent) followed by taper.	Monitor changes of renal function
	Grade 3 or 4	Permanently discontinue		
Myocarditis	Grade 1 or 2	Withhold	Based on severity of AE administer corticosteroids	Ensure adequate evaluation to confirm etiology and/or exclude other causes
	Grade 3 or 4	Permanently discontinue		
All other immune-related AEs ³	Intolerable/persistent Grade 2	Withhold	Based on type and severity of AE administer corticosteroids	Ensure adequate evaluation to confirm etiology and/or exclude other causes
	Grade 3	Withhold or discontinue based on the type of event. Events that require discontinuation include and not limited to: Gullain-Barre Syndrome, encephalitis		
	Grade 4 or recurrent Grade 3	Permanently discontinue		

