
1. Withhold or permanently discontinue pembrolizumab is at the discretion of the investigator or treating physician.
 
2. For grade 3 liver toxicity with elevated AST and/or ALT. Since HCC patients may have grade 1-2 elevation of AST/ALT at baseline, if these patients have Grade 3 elevation of AST/ALT, hold therapy and resume treatment when AST/ALT return to baseline or Grade ≤1. The AST/ALT should return to baseline or < 5 x ULN within 12 weeks from start of grade 3, otherwise patient should be discontinued from study.
 
3. Patients with intolerable or persistent Grade 2 drug-related AE may hold study medication at physician discretion. Permanently discontinue study drug for persistent Grade 2 adverse reactions for which treatment with study drug has been held, that do not recover to Grade 0-1 within 12 weeks of the last dose.
 
NOTE: For participants with Grade 3 or 4 immune-related endocrinopathy where withhold of pembrolizumab is required, pembrolizumab may be resumed when AE resolves to ≤ Grade 2 and is controlled with hormonal replacement therapy or achieved metabolic control (in case of T1DM).
				

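### After a first Grade 3 Guillain-Barré syndrome or encephalitis, Section 9.1.4 allows pembrolizumab to restart while Table 10.2 requires discontinuation, and no sentence says which text prevails

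*Combined protocol and SAP*

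**What the plan says.** **Section 9.1.4, Other Immune-Mediated Adverse Reactions.** The list of events includes "Guillain-Barré syndrome, vitiligo, encephalitis, and adrenal insufficiency". The next paragraph tells the investigator to withhold according to severity, give and taper corticosteroids, and then "Restart KEYTRUDA if the adverse reaction remains at Grade 1 or less". It ends with an instruction to permanently "discontinue KEYTRUDA for any severe or Grade 3 immune-mediated adverse reaction that recurs and for any life-threatening immune-mediated adverse reaction". No event type is excepted.

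**Table 10.2, All other immune-related AEs.** At Grade 3 the action is to withhold or discontinue according to the type of event: "Events that require discontinuation include and not limited to: Gullain-Barre Syndrome, encephalitis". The next row, "Grade 4 or recurrent Grade 3", is a permanent stop.

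**Table 10.2, NOTE.** For a Grade 3 or 4 immune-related endocrinopathy that required withholding, "pembrolizumab may be resumed when AE resolves to ≤ Grade 2 and is controlled with hormonal replacement therapy".

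**Which text governs dosing.** Section 8.4 refers the reader to Section 10.0 for dose modification. Section 10.1 says that intolerable Grade 2 and Grade 3 toxicities are managed by the table. Section 10.2 requires withholding as the table sets out. None of these mentions Section 9.1.4 or says what happens when the two differ.

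**The concern.** Both texts are current and both are written as instructions. For the same patient, with a first Grade 3 Guillain-Barré syndrome or encephalitis that has settled to Grade 1, one permits re-exposure and the other ends treatment. An investigator could follow the protocol's words and still do what another part of the protocol rules out, after a severe neurological immune event.

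There is a smaller consequence for reporting. Section 16.5 summarises the number of doses received and the reasons for discontinuation. For such a patient, both would depend on which section the site had used.

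**Working it through.** No design figure enters this point, so the check is a comparison of the two texts, event by event.

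| Situation | Section 9.1.4 | Table 10.2 | Result |
|---|---|---|---|
| First Grade 3 Guillain-Barré syndrome or encephalitis, improved to Grade 1 | Withhold, then restart | Requires discontinuation | Direct conflict |
| Recurrent Grade 3, other immune events | Permanent stop | Permanent stop | Agree |
| Life-threatening (Grade 4), other immune events | Permanent stop | Permanent stop | Agree |
| Grade 3 adrenal insufficiency, improved to Grade 2 on hormone replacement | Restart stated for Grade 1 or less | NOTE allows resumption | Ambiguous |
| First Grade 3 pneumonitis, nephritis or myocarditis | Permanent stop | Permanent stop | Agree |
| Grade 3 colitis | Withhold; silent on recurrence | Withhold; silent on recurrence | Agree, unless the general recurrence rule in 9.1.4 also applies |

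Three readings might remove the first conflict. None does.

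1. *Severe might be a separate trigger from recurrence in 9.1.4.* Elsewhere 9.1.4 equates severe with Grade 3. If severe alone were enough, the recurrence condition would have no effect.
2. *Discontinue in the table might mean a temporary hold.* The cell offers discontinuation as the alternative to withholding, so it cannot mean withholding.
3. *Restart at Grade 1 might itself be the error.* General instruction 2 of Table 10.2 also resumes at Grade 0 or 1 once corticosteroid has been tapered. The restart sentence therefore conflicts only for events that the table removes.

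**Size.** Inputs: each listed event occurred in less than 1% of patients in Trial 1 (Section 9.1.4); 28 evaluable and up to 35 enrolled patients (Section 16.4). Carrying the melanoma figure over to HCC is an assumption.

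- Expected number per event type, any grade: below 28 × 0.01 = 0.28 and below 35 × 0.01 = 0.35.
- Chance of at least one, 1 − (1 − p)^n. At the ceiling p = 0.01: 1 − 0.99^28 = 0.245 and 1 − 0.99^35 = 0.297. At an assumed p = 0.002: 0.055 and 0.068.

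These are any-grade figures. The conflict needs Grade 3 exactly, followed by recovery to Grade 1. The documents give no rate for that, so the relevant chance is lower by an unknown factor.

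**The case against.** The strongest reply is that Table 10.2 is plainly the operative text. Sections 8.4, 10.1 and 10.2 all send dosing to Section 10. Section 9.1.4 sits in the chapter on drug formulation and procurement, and its introduction describes its content as reference safety information. Section 11.0 also lets the investigator stop treatment for any event judged an unacceptable risk. Much of this stands: most readers would probably go to the table. But the pointers do not say that 9.1.4 yields. That section is headed as management of adverse events and is written in the imperative. The revision history for version 3.0 records safety text added to both sections, so 9.1.4 is maintained as working text.

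On adrenal insufficiency, the reply is that the NOTE is a permissive endocrine exception to a general rule, and that 9.1.4 does not say restart is allowed *only* at Grade 1. That is a fair reading. This part is an ambiguity, not a contradiction.

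A reader might also infer more than the documents support:

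- **That 9.1.4 as a whole stops only on recurrence.** It does not. It stops at the first Grade 3 pneumonitis or nephritis and at any grade of SJS or TEN, and for myocarditis it says "Permanently discontinue Pembrolizumab for grade 3-4 myocarditis or if toxicity does not resolve within 12 weeks of start of grade 2 toxicity".
- **That Table 10.2 re-treats recurrent Grade 3 colitis or AST/ALT elevation that 9.1.4 removes.** No row says so. Footnote 2 says "if these patients have Grade 3 elevation of AST/ALT, hold therapy and resume treatment when AST/ALT return to baseline or Grade ≤1", with a 12-week limit on recovery, and is silent on recurrence. A conflict arises only if the word any in 9.1.4 reaches beyond its Other heading. That reading is possible, because the pneumonitis paragraph refers forward to the general text and the table names recurrence in some rows but not in these. The scope needs stating; a contradiction is not shown.
- **That the two texts disagree on Grade 1 or 2 myocarditis.** Table 10.2 withholds, and 9.1.4 gives no hold instruction at those grades. That is silence.

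**Conclusion.** The conflict is real for one defined situation: a first Grade 3 Guillain-Barré syndrome or encephalitis, not life-threatening, that improves to Grade 1. The restart grade for adrenal insufficiency is a lesser ambiguity. The conclusion rests on reading both sections as current instructions and on the absence of any precedence sentence.

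Few patients, perhaps none, would meet the situation in a trial of 28 to 35. It matters because of what re-exposure could mean for that patient and because sites should dose consistently.

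It would be tempting to carry the argument through to the primary efficacy result, since one patient can decide 3 of 14 or 9 of 28. The documents do not support that as a material effect. Off-treatment imaging is scheduled (Section 12.3), and best overall response runs to progression or non-protocol therapy, not to the last dose (Section 14.5.4). Nor does the event drop out of the safety results. It is still recorded as an adverse event, and if treatment-related it counts towards the toxicity guideline in Section 17.2.2 whether or not dosing resumes. The Grade 3–4 AST (12%) and ALT (10%) rates cited in Section 1.1 for another anti-PD-1 agent cannot size the problem either: they are not recurrence rates, and those events are outside the firm conflict.

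**What to change.** - Reconcile the Other Immune-Mediated Adverse Reactions text of Section 9.1.4 with the All other immune-related AEs rows and the NOTE of Table 10.2, so that one action is stated for a first Grade 3 Guillain-Barré syndrome or encephalitis and one restart condition for Grade 3 adrenal insufficiency. The clinical team chooses the rule; this review takes no position on it.
- Add one sentence saying which section governs dosing when 9.1.4 and Table 10.2 differ.
- In the same edit, state whether the recurrence rule in 9.1.4 applies to events that have their own row in Table 10.2, such as colitis and AST/ALT elevation.

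The cost is wording in the next amendment, with no added visits, tests or patients.

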9.1.5 Serious Adverse Reactions Considered Expected for pembrolizumab

SOC	Adverse Reaction (MedDRA Preferred Terms)
Cardiac disorders	Autoimmune myocarditis Myocarditis
Endocrine disorders	Adrenal insufficiency Adrenocortical insufficiency acute Autoimmune thyroiditis Hyperthyroidism Hypophysitis Hypopituitarism Hypothyroidism Lymphocytic hypophysitis Secondary adrenocortical insufficiency Thyroid disorder Thyroiditis
Eye disorders	Autoimmune uveitis Iridocyclitis Iritis Ocular myasthenia Ocular sarcoidosis Uveitis
Gastrointestinal disorders	Autoimmune pancreatitis Colitis Colitis microscopic Diarrhoea Enterocolitis Enterocolitis haemorrhagic Oral lichen planus Pancreatitis Pancreatitis acute Pancreatitis necrotising
General disorders and administration	Pyrexia
Hepatobiliary disorders	Autoimmune hepatitis Drug-induced liver injury Hepatitis Hepatitis acute Hepatitis fulminant

Immune system disorders	Anaphylactic reaction Anaphylactoid reaction Cytokine release syndrome Drug hypersensitivity Hypersensitivity Sarcoidosis Serum sickness
Infections and infestations	Encephalitis Rash pustular
Injury, poisoning and procedural complications	Infusion related reaction
Metabolism and nutritional disorders	Diabetic ketoacidosis Fulminant type 1 diabetes mellitus Latent autoimmune diabetes in adults Type 1 diabetes mellitus
Musculoskeletal and connective tissue disorders	Immune-mediated necrotising myopathy Myopathy Myositis Psoriatic arthropathy Necrotising myositis Polymyositis Rhabdomyolysis
Nervous system disorders	Axonal neuropathy Demyelinating polyneuropathy Diabetic ketoacidotic hyperglycaemic coma Encephalitis autoimmune Guillain-Barre syndrome Limbic encephalitis Miller Fisher syndrome Myasthenia gravis Myasthenia gravis crisis Myasthenic syndrome
Renal and urinary disorders	Autoimmune nephritis Glomerulonephritis Glomerulonephritis membranous Nephritis Nephrotic syndrome Tubulointerstitial nephritis
Respiratory, thoracic and mediastinal disorders	Interstitial lung disease* Pneumonitis* Pulmonary sarcoidosis

Skin and subcutaneous tissue disorders	Acute febrile neutrophilic dermatosis Cutaneous sarcoidosis Dermatitis Dermatitis bullous Dermatitis exfoliative Drug eruption Drug reaction with eosinophilia and systemic symptoms Eczema Erythema multiforme Lichen planus Palmar-plantar erythrodysesthesia syndrome Pemphigoid Perivascular dermatitis Pruritus Psoriasis Rash Rash erythematous Rash generalised Rash macular Rash maculo-papular Rash morbilliform Rash papular Rash pruritic Skin disorder Skin necrosis Skin toxicity Stasis dermatitis Stevens-Johnson syndrome (SJS)* Subacute cutaneous lupus erythematosus Toxic epidermal necrolysis (TEN)*
For the purpose of safety reporting in clinical trials, only serious adverse reactions are considered expected. *Term also considered expected with fatal outcome.	

9.1.6 Composition

50 mg, lyophilized powder in single-use vial for reconstitution.

9.1.7 Storage Recommendations and Dosage Forms

Two Drug Product (DP) dosage forms are available for MK-3475: a white to off-white lyophilized powder, 50 mg/vial, and a liquid, DP 100 mg/vial, both in Type I glass vials intended for single use only.

- MK-3475 Powder for Solution for Infusion, 50 mg/vial (manufactured using the partially formulated DS), is reconstituted with sterile water for injection prior to use. MK-3475 DP is formulated with L-histidine as buffering agent,

polysorbate 80 as surfactant, sucrose as stabilizer/tonicity modifier, and hydrochloric acid (HCl) and/or sodium hydroxide (NaOH) for pH adjustment (if necessary).

- MK-3475 Solution for Infusion 100 mg/vial is a liquid DP (manufactured using the fully formulated DS with L-histidine as buffering agent, polysorbate 80 as surfactant, and sucrose as stabilizer/tonicity modifier), and has the identical formulation as that of the reconstituted lyophilized vial.

Both drug product dosage forms are stored under refrigerated conditions (2°C - 8°C). The product after reconstitution with sterile water for injection and the liquid drug product are a clear to opalescent solution which may contain proteinaceous and extraneous particulates. The reconstituted lyophilized product and the liquid product are intended for IV administration. The reconstituted DP solution or the liquid DP can be further diluted with normal saline or 5% dextrose in the concentration range of 1 to 10 mg/mL in IV containers made of polyvinyl chloride (PVC) or non-PVC material. Reconstituted vials should be immediately used to prepare the infusion solution in the IV bag and the infusion solution should be immediately administered. If not used immediately, vials and/or IV bags may be stored at 2-8 °C for up to a cumulative time of 20 hours. If refrigerated, the vials and/or IV bags should be allowed to equilibrate to room temperature prior to subsequent use. MK-3475 solutions may be stored at room temperature for a cumulative time of up to 4 hours. This includes room temperature storage of reconstituted or liquid DP solution in vials, room temperature storage of infusion solution in the IV bag and the duration of infusion. This recommendation is based on up to 24 hours of room temperature and up to 24 hours of refrigerated stability data of diluted pembrolizumab solutions in the IV bags.

9.1.8 Dispensation and Accountability

For this study, pembrolizumab (Keytruda®) will be provided by Merck as Pembrolizumab 50 mg (lyophilized powder for injection) or pembrolizumab 100 mg/ 4mL (solution for injection). Please see Appendix J for Preparation and Administration/ Reconstitution of Pembrolizumab (Keytruda®) for Injection (lyophilized powder)

(See also Section 8.3 Treatment Dispensation, Compliance and Accountability for Pembrolizumab)

10.0 TREATMENT/ DOSE MODIFICATIONS

10.1 Unacceptable Toxicity

Causality for all adverse events should be assessed and if deemed attributable, attempts should be made toward proper attribution.

Drug-related grade 4 toxicities will require subject to discontinue all study treatment. Intolerable grade 2 and grade 3 toxicities should be managed as per dose modification guidelines listed in the table below. Pembrolizumab therapy may be continued providing the residual adverse events are within permissible ranges for pembrolizumab dosing.

10.2 Dose Modification Guidelines for Pembrolizumab

Adverse events (AEs) both serious and non-serious associated with pembrolizumab exposure may represent an immunologic etiology. These AEs may occur shortly after the first dose or several months after the last dose of treatment. Pembrolizumab must be withheld for drug-related toxicities and severe or life-threatening AEs as per Table 10 below. See also Section 8.4 for supportive care guidelines and Appendix I.

Dosing interruptions are permitted in the case of medical/surgical events or logistical reasons not related to study therapy (e.g. elective surgery, unrelated medical events, patient vacation, and/or holidays). Subjects should be placed back on study therapy within 3 weeks of the scheduled interruption, unless otherwise discussed with the PI. The reason for the interruption should be documented in the patient's study record.

Table 10.2 Dose Modification and Toxicity Management Guidelines for Immune-related AEs Associated with Pembrolizumab

General instructions:				

 1. Corticosteroid taper should be initiated upon AE improving to Grade 1 or less and continue to taper over at least 4 weeks. 2. For situations where pembrolizumab has been withheld, pembrolizumab can be resumed after AE has been reduced to Grade 1 or 0 and corticosteroid has been tapered. Pembrolizumab should be permanently discontinued if AE does not resolve within 12 weeks of last dose or corticosteroids cannot be reduced to ≤ 10 mg prednisone or equivalent per day within 12 weeks. 3. For severe and life-threatening irAEs, IV corticosteroid should be initiated first followed by oral steroid. Other immunosuppressive treatment should be initiated if irAEs cannot be controlled by corticosteroids. 				
Immune-related AEs	Toxicity grade or conditions (CTCAEv4.0)	Action taken to pembrolizumab	irAE management with corticosteroid and/or other therapies	Monitor and follow-up
Steven-Johnson Syndrome (SJS)	Any	Permanently discontinue	Refer patient for specialized care for assessment and treatment.	If SJS confirmed, permanently discontinue pembrolizumab
Toxic Epidermal Necrolysis (TEN)	Any	Permanently discontinue	Refer patient for specialized care for assessment and treatment.	If TEN confirmed, permanently discontinue pembrolizumab
Pneumonitis	Grade 2	Withhold	Administer corticosteroids (initial dose of 1-2 mg/kg prednisone or equivalent) followed by taper	Monitor participants for signs and symptoms of pneumonitis Evaluate participants with suspected pneumonitis with radiographic imaging and initiate corticosteroid treatment Add prophylactic antibiotics for opportunistic infections
	Grade 3 or 4, or recurrent Grade 2	Permanently discontinue		
Diarrhea / Colitis	Grade 2 or 3	Withhold	Administer corticosteroids (initial dose of 1-2 mg/kg prednisone or equivalent) followed by taper	
 • Monitor participants for signs and symptoms of enterocolitis (ie, diarrhea, abdominal pain, blood or mucus in stool with or without fever) and of bowel perforation (ie, peritoneal signs and ileus). • Participants with \geq Grade 2 diarrhea suspecting colitis should consider GI consultation and performing endoscopy to rule out colitis. • Participants with diarrhea/colitis should be advised to drink liberal quantities of clear fluids. If sufficient oral fluid intake is not feasible, fluid and electrolytes should be substituted via IV

	Grade 4	Permanently discontinue		infusion.
AST / ALT elevation	3	Withhold	Administer corticosteroids (initial dose of 0.5- 1 mg/kg prednisone or equivalent) followed by taper	Monitor with liver function tests (consider weekly or more frequently until liver enzyme value returned to baseline or is stable
	4	Permanently discontinue --see exception below ²	Administer corticosteroids (initial dose of 1-2 mg/kg prednisone or equivalent) followed by taper	
Increased bilirubin	Grade 2	Withhold	Administer corticosteroids (initial dose of 0.5- 1 mg/kg prednisone or equivalent) followed by taper	Monitor with liver function tests (consider weekly or more frequently until liver enzyme value returned to baseline or is stable
	Grade 3 or 4	Permanently discontinue	Administer corticosteroids (initial dose of 1-2 mg/kg prednisone or equivalent) followed by taper	
Type 1 diabetes mellitus (T1DM) or Hyperglycemia	Newly onset T1DM or Grade 3 or 4 hyperglycemia associated with evidence of β -cell failure	Withhold	Initiate insulin replacement therapy for participants with T1DM Administer anti-hyperglycemic in participants with hyperglycemia	Monitor participants for hyperglycemia or other signs and symptoms of diabetes.
Hypophysitis	Grade 2	Withhold	Administer corticosteroids and initiate hormonal replacements as clinically indicated.	Monitor for signs and symptoms of hypophysitis (including hypopituitarism and adrenal insufficiency)
	Grade 3 or 4	Withhold or permanently discontinue ¹		

Hyperthyroidism	Grade 2	Continue	Treat with non-selective beta-blockers (eg, propranolol) or thionamides as appropriate	Monitor for signs and symptoms of thyroid disorders.
	Grade 3 or 4	Withhold or permanently discontinue ¹		
Hypothyroidism	Grade 2-4	Continue	Initiate thyroid replacement hormones (eg, levothyroxine or liothyronine) per standard of care	Monitor for signs and symptoms of thyroid disorders.
Nephritis and Renal dysfunction	Grade 2	Withhold	Administer corticosteroids (prednisone 1-2 mg/kg or equivalent) followed by taper.	Monitor changes of renal function
	Grade 3 or 4	Permanently discontinue		
Myocarditis	Grade 1 or 2	Withhold	Based on severity of AE administer corticosteroids	Ensure adequate evaluation to confirm etiology and/or exclude other causes
	Grade 3 or 4	Permanently discontinue		
All other immune-related AEs ³	Intolerable/persistent Grade 2	Withhold	Based on type and severity of AE administer corticosteroids	Ensure adequate evaluation to confirm etiology and/or exclude other causes
	Grade 3	Withhold or discontinue based on the type of event. Events that require discontinuation include and not limited to: Gullain-Barre Syndrome, encephalitis		
	Grade 4 or recurrent Grade 3	Permanently discontinue		

1. Withhold or permanently discontinue pembrolizumab is at the discretion of the investigator or treating physician.
 
2. For grade 3 liver toxicity with elevated AST and/or ALT. Since HCC patients may have grade 1-2 elevation of AST/ALT at baseline, if these patients have Grade 3 elevation of AST/ALT, hold therapy and resume treatment when AST/ALT return to baseline or Grade ≤1. The AST/ALT should return to baseline or < 5 x ULN within 12 weeks from start of grade 3, otherwise patient should be discontinued from study.
 
3. Patients with intolerable or persistent Grade 2 drug-related AE may hold study medication at physician discretion. Permanently discontinue study drug for persistent Grade 2 adverse reactions for which treatment with study drug has been held, that do not recover to Grade 0-1 within 12 weeks of the last dose.
 
NOTE: For participants with Grade 3 or 4 immune-related endocrinopathy where withhold of pembrolizumab is required, pembrolizumab may be resumed when AE resolves to ≤ Grade 2 and is controlled with hormonal replacement therapy or achieved metabolic control (in case of T1DM).
				

